7.5 Safety analysis

Safety endpoints include adverse events, vital signs, laboratory assessments, physical examination, and B-ultrasound. This analysis will be conducted in SA population.

7.5.1 Adverse events

AEs will be classified into standardized medical terminology from the verbatim description (investigator term) using the Medical Dictionary for Regulatory Activities (MedDRA). Verbatim description and MedDRA level terms, including the system organ class, preferred term, and lower level term, for all AEs will be presented in the data listings. In table summaries, the denominator for percentages will be the number of subjects in the treatment group within the safety analysis population. AEs are coded according to (MedDRA) version 17.0.

TEAE is defined as AE occurred on or after the first dose date of study drug. TEAEs will be presented by system organ class and preferred term. The subject level incidence is only one occurrence of a preferred term/system organ class per subject. If a subject reports multiple AEs under the same preferred term, then the count of subject level incidences for that preferred term will only be incremented by one. If a subject reports multiple AEs under the same system organ class, then the count of subject level incidences for that system organ class will also only be incremented by one. System organ classes will be presented in descending order of total frequency of subject level occurrences. Within each system organ class, preferred terms are presented in the same descending order of total frequency of subject level occurrences.

The following summaries of AEs will be provided:

- All AEs.
- All TEAEs.
- All treatment related TEAEs.
- All serious TEAEs.
- All non-serious TEAEs.
- All treatment related serious TEAEs.
- All TEAEs leading to permanent discontinuation of study drug.
- All TEAEs leading to permanent discontinuation from the study.
- All TEAEs that caused a change in dose or temporary interruption of study drug.

7.5.2 Vital sign

Vital signs including systolic blood pressure (mmHg), diastolic blood pressure (mmHg), pulse (beats/minute), respiratory rate (breaths/minute), body temperature (°C) and weight (kg) will be descriptively summarized by clinic visit. Changes from Baseline to each individual post-Baseline visit will also be presented.

7.5.3 Laboratory assessments

Results for clinical laboratory evaluations including: hematology, blood chemistry, blood coagulation, hepatitis B five items, pregnancy test, urinalysis and alpha fetoprotein (AFP) will be conducted at various visits as specified in the Study Schedule of the protocol. Descriptive statistics will be used for quantitative variables. For qualitative variables, the number and percentage for each

parameter will be presented.

Treatment-emergent grade 3 or grade 4 laboratory abnormalities are defined as values that increase at least one grade from baseline and get Grade 3 (severe) or 4 (potentially life threatening) at any post-baseline value. If the relevant baseline laboratory data are missing, then the screening laboratory result is used; if it is missing then any Grade 3 or 4 post-baseline values are considered treatment emergent.

The following summaries (number and percentage of subjects) of treatment-emergent laboratory abnormalities will be provided:

- Treatment-emergent Grade 3 or Grade 4 laboratory abnormalities
- Incidence of on-treatment hepatitis exacerbation defined as bilirubin ≥ 2 times ULN or albumin
 ≤ 3 g/dL or ALT ≥ 20 times ULN (and ≥ 2 times baseline)
- Confirmed (defined as two consecutive visits) increase in serum creatinine of 0.5 mg/dL above baseline
- Calculated creatinine clearance < 50 mL/min

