#### 201215

- 1 All results to be obtained before baseline visit.
- 2 No more than 6 days before or 6 days after the date scheduled based on the time from baseline visit not from the previous visit.
- 3 Demographic data includes birth date, gender and race
- 4 Medical history will include any acute and chronic medical conditions including prior surgery, information related to hepatitis B history, any current and prior HBV medications, and previous HBV-related procedures.
- 5 Update any new medical conditions and/or concomitant medications that have occurred since study screening.
- 6 Concomitant medications including traditional Chinese medicines and/or herbal remedies.
- 7 At screening, a complete physical examination will be performed. For all following indicated visits, a brief physical examination will be performed.
- 8 Including blood pressure, pulse, respiratory rate and temperature.
- 9 Urine pregnancy test will be performed at screening, baseline and every 3 months after dosing.
- 10 Tests will be performed at central lab.
- 11 B ultrasound examination include liver, pancreas, spleen, gall bladder and kidney.
- 12 Urinalysis: urine glucose, ketones, specific gravity, blood, pH and protein.
- 13 HBV DNA will be tested using Roche COBAS Taqman HBV test (LLD:20IU/ML).
- 14 Resistance surveillance will be performed at baseline or under the condition defined in protocol by direct sequencing of the polymerase gene. See Section 6.2.5
- 15 Each study visit: All study medication to be collected and reconciled.

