## 6.3.10. Serum Creatinine Elevation

Serum creatinine values  $\ge 0.5 \text{ mg/dL}$  above baseline should be confirmed by repeat testing within 3 calendar days of receipt of results.

For serum creatinine elevations  $\geq 0.5 \text{ mg/dL}$  above baseline, subjects may continue all study medication, but it is recommended that subjects be monitored weekly until the serum creatinine returns to the original baseline value or  $\leq 0.3 \text{ mg/dL}$  from baseline.

All study drugs should be permanently discontinued in the event that repeat testing of serum creatinine confirms >2.0 mg/dL. The subject should be followed weekly until the serum creatinine reaches within 0.3 mg/dL of the baseline value.

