## 11. **APPENDIX**

## 11.1. Appendix 1: Estimated Creatinine Clearance Rate (CLcr) Formula and Estimated Glomerular Filtration Rate (GFR) Equation

Creatinine clearance rate(CLcr) using Cockcroft-Gault (CG) formula:

CLcr=[(140-Age)×Ideal Body Weight(kg)]/[72×Scr(mg/dl)]

Scr=Serum Creatinine in mg/dl; for femal Multiplied by the coefficient of 0.85

Note: If actual body weight(ABW) is lower than ideal body weight (IBW), ABW should be used.

Calculation Formula for IBW:

(Male)IBW=50kg+2.3kg×[Height(Inches)-60]

(Female)IBW=45.5kg+2.3kg×[Height(Inches)-60]

1Inch=2.54cm

Glomerular filtration rate is estimated by Chronic kidney disease (CKD)-Epidemiology Collaboration (EPI) equation:

GFR(mL/min per 1.73 m^2) =  $141 \times \min(\text{Scr/}\kappa, 1)^{\alpha} \times \max(\text{Scr/}\kappa, 1)^{-1.209} \times 0.993^{\text{Age}}$  [ × 1.018 if female] [ × 1.159 if black],

where Scr is serum creatinine (mg/dl),  $\kappa$  is 0.7 for females and 0.9 for males,  $\alpha$  is -0.329 for females and -0.411 for males, min is the minimum of Scr/ $\kappa$  or 1, and max is the maximum of Scr/ $\kappa$  or 1

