7.4.2 Analysis of secondary variables

Analysis for secondary variable of the log₁₀ reduction in serum HBV DNA by patterns of mutation and overall per visit will be summarized by descriptive statistics as the mean, standard deviation, two-sided 95%CI, minimum, median, maximum, and the number of observations. The patterns of mutation will be summarized by 2 categories. One includes wild-type, LAM-R, ADV-R and ETV-R. The other one includes wild-type, ADV-R single mutation (A181T/V; N236T), ADV-R double mutation (A181T/V+N236T)) and other mutation. Nominal P values between different patterns of mutation will be provided at week 24, 48, 96, 144. Individual HBV DNA levels of subjects with genotypic resistance to ADV (A181T/V+N236T) will be summarized over time by figure.

In addition, the number and percentage will be presented respectively for secondary variables including:

- The proportion of subjects with virological response (serum HBV DNA <20 IU/mL and serum HBV DNA <69 IU/mL, separately) by visit
- The proportion of subjects with virological response (serum HBV DNA <20 IU/mL and serum HBV DNA <69 IU/mL, separately) by visit in the subgroup with confirmed multi-drug resistance at baseline
- The proportion of subjects with virological response(serum HBV DNA <20 IU/mL and serum HBV DNA <69 IU/mL, separately) by visit in the subgroup with medical history (previously exposed to ADV >6 months or not, ETV >6 months or not) (Subjects with ETV >6 months will be separated as ETV-R and non ETV-R)
- The proportion of subjects achieving HBeAg loss, HBeAg seroconversion, HBsAg loss and

HBsAg seroconversion at Week 48, 96 and 144 for HBeAg positive subjects

- The proportion of subjects achieving HBsAg loss and HBsAg seroconversion at Week 48, 96 and 144 for HBeAg negative subjects
- The proportion of subjects with ALT normalization at week 48, 96 and 144 in subjects who have abnormal ALT at baseline
- The incidence of subjects who experience viral breakthrough (defined as 1 log increase in HBV DNA from nadir determined by two sequential HBV DNA measurements) overall and by each visit.
- The proportion of subject with unsatisfactory response, overall and by each visit. Unsatisfactory response is defined as subjects who have HBV DNA ≥200 IU/mL at week 48 and afterwards have ≤1 log10 IU/mL decrease in HBV DNA at two consecutive tests, confirmed by a third visit (additional visit) at least one month apart
- Mutation pattern change from baseline at week 48, 96, 144

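### The eGFR and phosphorus figures are listed on PP and mITT instead of SA, and the SAP 7.5.3 creatinine row can omit rises that the protocol's repeat test confirmed

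*SAP*

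**What the plan says.** **Populations.** SAP 4 and SAP 7.5 assign safety endpoints, laboratory assessments included, to SA: at least one dose and at least one post-baseline safety assessment. In SAP 9, mean change in eGFR is listed on mITT (Figure 5.3.1) and PP (5.3.2), and mean change in serum phosphorus on mITT (5.3.3) and PP (5.3.4). None of the four is on SA. PP is mITT without major deviators. SAP 7.1 lists use of prohibited medication as a deviation category and leaves it to the study team, before final lock, to decide which deviations are major. Protocol 5.6.2, the section on prohibited medication, covers nephrotoxic agents.

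**Creatinine.** One row in SAP 7.5.3 is "Confirmed (defined as two consecutive visits) increase in serum creatinine of 0.5 mg/dL above baseline". The same section says that laboratory evaluations "will be conducted at various visits as specified in the Study Schedule of the protocol". Protocol 6.3.10 says that a value at least 0.5 mg/dL "above baseline should be confirmed by repeat testing within 3 calendar days of receipt of results". For such rises "it is recommended that subjects be monitored weekly until the serum creatinine returns to the original baseline value", or to within 0.3 mg/dL of it. The SAP does not say whether the repeat or a weekly check is a visit. In SAP 7.4.2 it does use the word for an unscheduled HBV DNA test: unsatisfactory response is "confirmed by a third visit (additional visit) at least one month apart".

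**The concern.** Renal toxicity is the first risk in the protocol's risk table, so these are the renal outputs a reader will look at. A PP population is built for efficacy. In a renal safety plot it can remove the subjects whose co-medication raises their renal risk. SAP 3.1 says that key outputs go out annually for publication. In the text available to us, the annual-output mark stands beside the PP versions of these figures and not beside the mITT versions.

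For creatinine, two programmers could read the word visit differently and report different percentages from the same data. On the scheduled-visit reading, the row leaves out events that the protocol's own procedure had confirmed.

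**Working it through.** The plan states no figure for this point, so there is none to reproduce.

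**1. Who appears in each figure.** mITT needs one dose; SA needs one dose and a post-baseline safety assessment. A subject adds a post-baseline change in eGFR or phosphorus only if there is a post-baseline laboratory value, which is itself a safety assessment. The contributors to an mITT change plot and an SA change plot should therefore coincide. PP differs from both by whoever the study team judges a major deviator.

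**2. Visit spacing.** Visits are 12 weeks (84 days) apart. Under footnote 2 of protocol Table 1 each may fall "No more than 6 days before or 6 days after the date scheduled based on the time from baseline visit".
- Shortest gap: 84 − 6 − 6 = 72 days; 72/7 = 10.3.
- Longest gap: 84 + 6 + 6 = 96 days; 96/7 = 13.7.

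So 10 to 13 of the recommended weekly checks fit between two scheduled visits, which leaves ample room for a confirmed rise to resolve.

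**3. Which patterns count.** Take a first rise at scheduled visit A, then the repeat, then scheduled visit B.

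| Repeat | Visit B | Scheduled visits only | Next available result | Repeat or next scheduled visit |
|---|---|---|---|---|
| high | high | yes | yes | yes |
| high | not high | **no** | yes | yes |
| not high | high | yes | **no** | yes |
| not high | not high | no | no | no |

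The second line is the gap. The third shows that a next-available-result rule would lose A–B pairs that the scheduled-visit reading counts. Only the either/or rule keeps both.

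**4. Do other numeric rows catch the gap?** In SAP 8.2 creatinine is Grade 1 above 1.5 mg/dL and Grade 3 above 3.0 mg/dL, and only Grades 3 and 4 are summarised. The other renal row is creatinine clearance below 50 mL/min. Protocol Appendix 1 gives CLcr = (140 − age) × IBW / (72 × Scr), times 0.85 for women. The examples assume actual weight at or above ideal weight and baseline CLcr of at least 70.
- Man, 170 cm: IBW = 50 + 2.3 × (170/2.54 − 60) = 65.94 kg. At age 40, 0.9 mg/dL gives 100 × 65.94/64.8 = 101.8, and 1.4 mg/dL gives 100 × 65.94/100.8 = 65.4. At 1.4 he stays at or above 50 for ages 18 to 63.
- Woman, 160 cm: IBW = 45.5 + 2.3 × (160/2.54 − 60) = 52.38 kg. At age 35, 0.7 mg/dL gives 105 × 52.38 × 0.85/50.4 = 92.8, and 1.2 mg/dL gives 105 × 52.38 × 0.85/86.4 = 54.1. At 1.2 she stays at or above 50 for ages 18 to 42.

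Both rises are exactly 0.5 mg/dL, below Grade 1, and outside the clearance row. Large rises are different: at 2.1 mg/dL the same man has 115 × 65.94/151.2 = 50.2 at age 25 and 114 × 65.94/151.2 = 49.7 at age 26, so the clearance row catches nearly all such cases. The gap concerns moderate, transient rises.

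**The case against.** **On creatinine**, protocol 6.3.10 governs clinical follow-up and SAP 7.5.3 defines a tabulation, so the two may differ without contradiction. The scheduled-visit reading is the natural one: the section ties results to the study schedule, and the only additional-visit column in protocol Table 1 is for unsatisfactory response to TDF. Counting only sustained rises is a legitimate choice. Visit handling may also be settled in the table shells, which are a separate document. All of this stands, and it makes the point one of completeness. It does not alter what the row leaves out on that reading.

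**On populations**, the mITT figures already show what SA would, loss from PP depends on a decision not yet made, and the annual-output column may have been misaligned when the PDF was read. That also stands. The mismatch with SAP 4 and 7.5 remains. Creatinine and phosphorus should still appear in the SA chemistry table (Table 5.3.2), but no listed title names eGFR on SA.

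**A stronger reading about the liver row.** A reader might infer that the hepatitis exacerbation row in SAP 7.5.3 mainly counts Grade 1–2 albumin or bilirubin changes and loses the protocol's ALT flares. The documents do not support that. Bilirubin at 2 × ULN or more is never Grade 1, albumin is Grade 1 only at exactly 3.0 g/dL, and the row also takes in Grade 3 and 4 values. No flare (ALT above 10 × ULN and above twice baseline) escapes both ALT summaries. With baseline at or below 10 × ULN it is a treatment-emergent Grade 4. With a higher baseline, twice baseline exceeds 20 × ULN and meets the row's ALT arm. A grid of 8,660 flare combinations gave 0 missed. Nothing obliges the SAP to tabulate the protocol 6.3.1 management categories.

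One unclear bracket remains: "ALT ≥ 20 times ULN (and ≥ 2 times baseline". It cannot apply to albumin, since 2 × 3.2 = 6.4 g/dL is above the 3 g/dL limit. Whether it reaches bilirubin is unstated. From a baseline of 1.5 × ULN, the value needed is 2.0 × ULN if it does not, and 2 × 1.5 = 3.0 × ULN if it does.

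**Conclusion.** The point holds, as a minor one, in two parts.

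First, the population of the four renal and phosphorus figures conflicts with SAP 4 and 7.5. Bias is possible only in the PP versions, and only if nephrotoxic co-medication is judged a major deviation. It would be wrong to infer that the plan hides renal data, because the mITT versions should show essentially the SA subjects.

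Second, if only scheduled visits count, the creatinine row omits rises confirmed by the protocol repeat that resolve within the 72 to 96 days to the next visit. It would be wrong to infer that these events vanish: adverse event summaries and SA listings may show them.

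The documents give no rate of creatinine rise or of prohibited medication, so the number of subjects affected cannot be estimated. The primary endpoint is not affected.

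**What to change.** 1. In SAP 9, produce the eGFR and phosphorus figures on SA and use the SA version in the annual outputs. Any PP version should be supplementary only. Check the annual-output column against the SAP's own table.
2. In SAP 7.5.3, count a rise of at least 0.5 mg/dL as confirmed if it is met again either at the protocol 6.3.10 repeat or at the next scheduled visit. Compared with the scheduled-visit reading, this can only add events.
3. Optionally, state whether the twice-baseline condition applies to ALT only.

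The cost is SAP wording, a population label and minor reprogramming; creatinine counts may be slightly higher. One check comes first: repeat results must reach the database. Protocol 6.3.11 requires additional local results in the CRF only if they change management or are judged clinically significant, so without that check the new row could rest on selectively recorded repeats. These are tabulation changes only; no clinical threshold or follow-up rule changes.

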7.5.4 Physical examination

The result of physical examination will be categorized as "Not Done", "Normal" or "Abnormal". The detailed information including date of physical examination and the result of body system for each subject will be presented in the listing.

7.5.5 B-ultrasound

B-ultrasound examination include sliver, pancreas, spleen, gall bladder and kidney. It is assessed based on 3-level system (normal, abnormal not clinically significant, or abnormal clinically significant). All B-ultrasound data will be presented in the listing.

3	Exclusion	Creatinine clearance less than 70 ml/min.
4	Englasian	Alanine aminotransferase >10 times ULN at screening or history of acute exacerbation
4 Exclusion		leading to transient decompensation.
5	Exclusion	Haemoglobin <8g/dL, absolute neutrophil count <1.0 x 109/L, platelets <75 x 109/L.
		Documented co-infection with hepatitis A (HAV), hepatitis C (HCV), hepatitis delta
6	T al al a	virus (HDV), hepatitis E virus (HEV) or HIV. For HCV co-infection, subjects who are
0	Exclusion	anti-HCV positive and in whom HCV RNA is undetectable are considered to be not
		eligible for enrolment.
7	F 1	Evidence of active liver disease due to autoimmune hepatitis (antinuclear antibody
/	Exclusion	titre >1:160)
		Any serious or active medical or psychiatric illnesses other than hepatitis B which, in
		the opinion of the Investigator, would interfere with subject treatment, assessment or
0	Englasian	compliance with the protocol. This would include any uncontrolled clinically
8	Exclusion	significant renal, cardiac, pulmonary, vascular, neurogenic, digestive, metabolic
		(diabetes, thyroid disorders, adrenal disease), immunodeficiency disorders,
		pathological fractures or cancer.
		Active alcohol or drug abuse or history of alcohol or drug abuse considered by the
9	Exclusion	Investigator to be sufficient to hinder compliance with treatment, participation in the
		study or clinical significance of results.
10	Exclusion	A female who is breastfeeding or plan to breast.
		Use of immunosuppressive therapy, immunomodulatory therapy (including PEG-IFN
11	Exclusion	and short-acting interferon or thymosin ,), systemic cytotoxic agents within the
		previous 6 months prior to screening.
12	Exclusion	Planned for liver transplantation or previous liver transplantation.
13	Exclusion	Receipt of TDF within 6 months prior to screening.
		Therapy with nephrotoxic drugs (e.g., aminoglycosides, amphotercin B, vancomycin,
1.4	Englasian	cidofovir, foscarnet, cis-platinum, pentamidine etc.) or competitors of renal excretion
14	Exclusion	(e.g., probenecid) within 2 months prior to study screening or the expectation that
		subject will receive any of these during the course of the study.
15	Evolution	History of hypersensitivity to nucleoside and/or nucleotide analogues and/or any
15	Exclusion	component of study medication.
16	Exclusion	Inability to comply with study requirements as determined by the study Investigator.

8.2 Treatment-emergent Laboratory Abnormalities Grading Scale

Hematology					
	Grade 1	Grade 2	Grade 3	Grade 4	
	10.0 to 10.9 g/dL	9.0 to < 10.0 g/dL	7.0 to < 9.0 g/dL	< 7.0 g/dL	
	100 to 109 g/L	90 to < 100 g/L	70 to < 90 g/L	< 70 g/L	
	OR	OR	OR		
Hemogolobin	Any decrease from	Any decrease from	Any decrease from		
	baseline	baseline	baseline		
	2.5 to < 3.5 g/dL	3.5 to < 4.5 g/dL	\geq 4.5 g/dL		
	25 to < 35 g/L	35 to < 45 g/L	\geq 45 g/L		
Neutrophil (ANC)	1000 to 1300 /mm ³	750 to $< 1000 \ /mm^3$	500 to $< 750 \ /mm^3$	< 500 /mm ³	
Neutrophii (ANC)	1.00 to 1.30 GI/L	0.75 to < 1.00 GI/L	0.50 to < 0.75 GI/L	< 0.50 GI/L	
T multiple to	600 to 650 /mm ³	500 to $< 600 \ /mm^3$	$350 \text{ to} < 500 / \text{mm}^3$	< 350 /mm ³	
Lymphocyte	0.60 to 0.65 GI/L	0.50 to < 0.60 GI/L	0.35 to < 0.50 GI/L	< 0.35 GI/L	
	100,000 to < 125,000	50,000 to <	25,000 to <	< 25.000 /	
Platelets	/mm ³	100,000 /mm ³	50,000 /mm ³	< 25,000 /mm ³	
	100 to < 125 GI/L	50 to < 100 GI/L	25 to < 50 GI/L	< 25 GI/L	
W1.1. D1 1.C.11	2000 to 2500 /mm ³	1500 to $< 2000 \ /mm^3$	$1000 \text{ to} < 1500 / \text{mm}^3$	< 1000 /mm ³	
white Blood Cell	2.00 to 2.50 GI/L	1.50 to < 2.00 GI/L	1.00 to < 1.50 GI/L	< 1.00 GI/L	
Blood Chemistry	·		·		
ALT (SGOT)	1.25 to 2.50×ULN	> 2.50 to 5.00 × ULN	> 5.00 to 10.0 × ULN	$> 10.0 \times ULN$	
AST (SGPT)	1.25 to 2.50×ULN	> 2.50 to 5.00 × ULN	> 5.00 to 10.0×ULN	$> 10.0 \times ULN$	
Alkaline	1.05 (
Phosphatase	$1.25 \text{ to } 2.50 \times \text{ULN}$	> 2.50 to $5.00 \times ULN$	> 5.00 to $10.0 \times ULN$	$> 10.0 \times ULN$	
4.11	3.0 g/dL to < LLN	2.0 to < 3.0 g/dL	< 2.0 g/dL		
Albumin	30 g/L to < LLN	20 to < 30 g/L	< 20 g/L	NA	
	130 to 135 mEq/L	125 to < 130 mEq/L	121 to < 125 mEq/L	< 121 mEq/L	
Hyponatremia	130 to 135 mmol/L	125 to < 130 mmol/L	121 to < 125 mmol/L	<121 mmol/L	
	146 to 150 mEq/L	> 150 to 154 mEq/L	> 154 to 159 mEq/L	> 159 mEq/L	
Hypernatremia	146 to 150 mmol/L	> 150 to 154 mmol/L	>154 to 159 mmol/L	>159 mmol/L	
TT 1.1 .	3.0 to 3.4 mEq/L	2.5 to < 3.0 mEq/L	2.0 to < 2.5 mEq/L	< 2.0 mEq/L	
Нурокајета	3.0 to 3.4 mmol/L	2.5 to < 3.0 mmol/L	2.0 to < 2.5 mmol/L	< 2.0 mmol/L	
	5.6 to 6.0 mEq/L	> 6.0 to 6.5 mEq/L	> 6.5 to 7.0 mEq/L	> 7.0 mEq/L	
Hyperkalemia	5.6 to 6.0 mmol/L	> 6.0 to 6.5 mmol/L	> 6.5 to 7.0 mmol/L	> 7.0 mmol/L	
Hypoglycemia	55 to 64 mg/dL	40 to < 55 mg/dL	30 to < 40 mg/dL	< 30 mg/dL	
(Fasting)	3.03 to 3.58 mmol/L	2.20 to < 3.03 mmol/L	1.64 to < 2.20 mmol/L	< 1.64 mmol/L	
